#### **6.2.3 Administration of ketamine**

- To be administered by a medical doctor or nurse
  - Double check of dose/volume to be administered to the patient
- Intramuscular administration
  - Doses can range 0.5-1.2 mg/kg. Starting dose for all participants will be 0.5mg/kg.
  - Dose can be titrated up to maximum of 1.2 mg/kg or titrated down to 0.5 mg/kg based on response and clinical judgement.
  - Dose will be administered by injecting into large muscle mass (eg, deltoid, gluteal muscle, thigh)

#### 6.2.4 Monitoring after administration

- During KAP session
  - Check blood pressure 40 minutes and 2 hours after ketamine administration
    - Give clonidine 0.1 mg po in clinic if blood pressure is greater than 180/110. If blood pressure remains elevated 1 hour after clonidine administration, transfer patient to a higher level of care.
    - Initiate emergency response procedures if blood pressure is greater than 180/110 and the patient develops symptoms of hypertensive crisis (eg, headache, vision changes)
  - Severe emotional distress or agitation as determined by MD.
    - Lorazepam 0.5 mg po/im will be available on demand. This may be repeated once after one hour for ongoing severe emotional distress or agitation.
  - Check respiratory rate at 40 minutes and 2 hours after ketamine administration
    - Initiate emergency response procedures and start continuous oxygen saturation monitoring if respiratory rate is < 8 breaths per minute or obtunded
    - Oxygen per nasal cannula available for oxygen saturation < 92%
    - Bag ventilation available
  - Nausea or vomiting
    - Ondansetron 4 mg po/im will be available on demand. This may be repeated once after one hour for ongoing nausea and vomiting.
- Following 3-hour KAP session
  - The patient must have an adult escort with them for at least 3 hours post-treatment
  - The medical doctor or medical assistant will assess for suicidal ideation or other safety concerns
  - The patient must avoid driving and operating machinery for at least 12 hours post-treatment
- Patient must meet the following objective criteria prior to leaving clinic ( $\geq$  2 hours following ketamine administration)
  - Patient must have oxygen saturation  $>$  92% on room air
  - Patient must have respirations  $>$  8 breaths per minute
    - Patient must be able to take a deep breath and cough.
  - Patient must have systolic blood pressure  $+$ / $-$  20 mmHg of pre-administration measurement
  - Patient must be fully awake
  - Patient must be able to move all extremities

Ketamine is stored at the HMHI KAP Clinic and administered by an MD study investigator. The HMHI KAP Clinic employs a log of ketamine administration in accordance with DEA standards. Appropriate records will be kept to accurately show all dispensing activities including the return of any unused Investigational Product (IP). IP will be supplied only to subjects deemed eligible for study therapy. IP may not be dispensed to patients who have not been enrolled in the trial.

Patients will be advised to refrain from the following for 24 hours before ketamine:

- Cannabis
- Alcoholic beverages
- Psychoactive drugs
- Non-routine PRN medications
- Grapefruit, grapefruit juice, and other CYP4A inhibitors

On the day of ketamine administration, patients on opioids should not take any long-acting opioids within 6 hours prior to or 6 hours proceeding ketamine administration. Patients should consume approximately the same amount of caffeine-containing beverage (e.g., coffee, tea) that he/she consumes on a usual morning, before arriving at the research unit. If the subject does not routinely consume caffeinated beverages, he or she must agree not to do so on the day of ketamine administration. Patients should also not use nicotine for at least 2 hours before ketamine administration.

All doses of ketamine will be administered at the investigational site by qualified medical staff. The time of administration will be recorded in the patients' research charts. Any reason for deviation from the protocol-specified dose or schedule will be documented in the subject's research chart.

### **6.2.5 Accountability and Compliance**

Ketamine is currently stored at the HMHI KAP Clinic in a secure and locked medication safe in accordance with DEA standards and is overseen by HMHI Pharmacy staff with regular inspections. This involves logging of dose, bottle # of ketamine, patient MRN, and amount of ketamine wasted per administration day with signatures of 2 clinic members present to observe the wasting of medication.

## **6.3 Ketamine**

### **6.3.1 Investigational Product Supplies**

Ketamine will be sourced from the current commercial supply stored at the HMHI KAP Clinic.

### **6.3.2 Preparation and Dispensing**

The investigator or qualified personnel will prepare and dispense all investigational supplies. Appropriate records will be kept to accurately show all dispensing activates and Investigational Product (IP) will be supplied only to subjects deemed eligible for study therapy. IP may not be dispensed to subjects who have not been enrolled in the trial.

The time of administration will be recorded in the patients' research charts. Any reason for deviation from the protocol-specified dose or schedule will be documented in the subject's research chart.

## **6.4 Adverse Event Management**

Adverse events will be managed as outlined in Section 6.1.4.

## 6.5 Supportive Care

All supportive measures consistent with optimal patient care may be given throughout the study as deemed necessary by the treating investigator.

## 6.6 Concomitant Medications and Therapies

All supportive measures consistent with optimal subject care may be given throughout the study.

All administered concomitant medications (including herbal supplements) and non-medicinal therapies (including transfusions) used 28 days prior to registration, and until 30 days after the last dose of study therapy will be recorded in the subject's research chart and corresponding eCRF, if applicable.

### 6.6.1 Prohibited Therapy

Medications or vaccinations specifically prohibited in the exclusion criteria are not allowed during the active treatment period. Patients are prohibited from receiving the following therapies during the treatment phase of this trial:

- Other investigational agents
- Herbal remedies known to potentially interfere with major organ function (e.g., hypericin)
- Monoamine oxidase inhibitors
- Sedatives – any opioid, benzodiazepine, sedative hypnotic, or alcohol
- Theophylline or Aminophylline
- Sympathomimetics (excluding albuterol) and Vasopressin

Patients will be advised to refrain from the following for 12 hours before ketamine:

- Cannabis
- Psychostimulants-includes methylphenidate, any amphetamines, modafinil, or armodafinil
- Non-routine PRN medications

On the day of ketamine administration, patients on opioids should not take any long-acting opioids within 12 hours prior to or 6 hours proceeding ketamine administration. Patients should consume approximately the same amount of caffeine-containing beverage (e.g., coffee, tea) that he/she consumes on a usual morning, before arriving at the research unit. If the subject does not routinely consume caffeinated beverages, he or she must agree not to do so on the day of ketamine administration. Patients should also not use nicotine for at least 2 hours before ketamine administration. .

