### 5.1 Inclusion Criteria

1.  Subject aged  $\geq$  18 years.
2.  Subjects with non-operable GI cancers requiring multi-modal treatment (e.g. surgery +/- chemo +/-radiation) and have a high likelihood of recurrence and/or treatment failure in the opinion of the treating investigator.
3.  Screen positivity for existential distress on the EDS, defined as scoring  $\geq$  3 on any of the 10 component domains, or a total score  $\geq$  6
4.  ECOG Performance Status  $\leq$  2.
5.  Adequate hepatic function as defined as:
  - Total Bilirubin  $\leq$  1.5x institutional upper limit of normal (ULN) unless elevated bilirubin is related to Gilbert's Syndrome
  - AST(SGOT)/ALT(SGPT)  $\leq$  3  $\times$  institutional ULN
    - Subjects with liver metastases will be allowed to enroll with AST and ALT levels  $\leq$  5  $\times$  ULN.
6.  For subjects of childbearing potential: Negative pregnancy test or evidence of post-menopausal status. The post-menopausal status will be defined as having been amenorrheic for 12 months without an alternative medical cause. The following age-specific requirements apply:
  - Subjects  $<$  50 years of age:
    - Amenorrheic for  $\geq$  12 months following cessation of exogenous hormonal treatments; and
    - Luteinizing hormone and follicle-stimulating hormone levels in the post-menopausal range for the institution; or
    - Underwent surgical sterilization (bilateral oophorectomy or hysterectomy).
  - Subjects  $\geq$  50 years of age:
    - Amenorrheic for 12 months or more following cessation of all exogenous hormonal treatments; or
    - Had radiation-induced menopause with last menses  $>1$  year ago; or

- Had chemotherapy-induced menopause with last menses >1 year ago; or
- Underwent surgical sterilization (bilateral oophorectomy, bilateral salpingectomy, or hysterectomy).

7.  Subjects of childbearing potential and subjects with a sexual partner of childbearing potential must agree to use a highly effective method of contraception as described in Section 5.3.1.

8.  Subjects with a sexual partner of childbearing potential must agree to use a condom during intercourse for 24 hours post- ketamine dose.

9.  Agree to refrain from using any psychoactive drugs, including alcoholic beverages, ondansetron, cannabis, and non-routine PRN medications within 24 hours of each ketamine administration. Exceptions include daily use of caffeine, nicotine, and opioid pain medication (see Section 6.5.1).

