10.  Able to provide informed consent and willing to sign an approved consent form that conforms to federal and institutional guidelines.

11.  Agree that for one week preceding the ketamine session, he/she will refrain from taking any nonprescription medication, nutritional supplement, or herbal supplement except when approved by the research team. Exceptions will be evaluated by the research team and will include acetaminophen, non-steroidal anti-inflammatory drugs, and common doses of vitamins and minerals.

12.  Agree not to use nicotine for at least 2 hours before the ketamine administration or for the duration of the ketamine session.

13.  Agree to consume approximately the same amount of caffeine-containing beverage (e.g., coffee, tea) that he/she consumes on a usual morning, before arriving at the research unit on the morning of the ketamine session. If the subject does not routinely consume caffeinated beverages, he or she must agree not to do so on the day of ketamine administration.

14.  Subjects requiring opioid use for pain are on a stable pain management regimen or do not experience clinically significant sedation during opioid use.

- Note: Long-acting opioid medications (e.g., oxycodone sustained-release, morphine sustained release) will be allowed if the last dose occurred at least 6 hours before ketamine administration; such medication will not be taken again until at least 6 hours after ketamine administration.

15.  Fluent in English.

16.  Reading literacy and comprehension sufficient for understanding the consent form and study questionnaires, as evaluated by study staff obtaining consent.

17.  Have a support person who is be able to escort the subject home from the ketamine dosing sessions.

- Note: The use of ride services will not be permitted (e.g., Uber, Lift, taxi, etc.)

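### Section 6.6.1 bans every opioid during the treatment phase, although inclusions 9 and 14 admit patients on opioid pain medication; its long-acting interval and the pointers to it also need correcting

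*Combined protocol and SAP*

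**What the plan says.** **The ban.** Section 6.6.1 lists therapies that patients may not receive during the treatment phase. The sedatives bullet covers "any opioid, benzodiazepine, sedative hypnotic, or alcohol". The phase is not defined, and the bullet has no exception for analgesia.

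**The permissions.** Inclusion 9 asks patients to "refrain from using any psychoactive drugs, including alcoholic beverages, ondansetron, cannabis, and non-routine PRN medications within 24 hours of each ketamine administration" and then lists exceptions: "Exceptions include daily use of caffeine, nicotine, and opioid pain medication (see Section 6.5.1" is the text, with its cross-reference. Inclusion 14 begins "Subjects requiring opioid use for pain are on a stable pain management regimen" and offers, as an alternative, opioid use without clinically significant sedation. Its note says that long-acting products "will be allowed if the last dose occurred at least 6 hours before ketamine administration", and lets them resume 6 h afterwards.

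**The timing rules.** Later in the same Section 6.6.1, "patients on opioids should not take any long-acting opioids within 12 hours prior to or 6 hours proceeding ketamine administration". The closing text of Section 6.2.4 gives the same rule with 6 h before ketamine instead of 12 h. For cannabis and non-routine PRN drugs, 6.6.1 says "Patients will be advised to refrain from the following for 12 hours before ketamine", while inclusion 9 and the end of 6.2.4 say 24 h.

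**The concern.** A patient cannot be barred from every opioid and at the same time be on opioids under a timing rule. Site staff therefore get opposite answers to two practical questions: may a patient on opioid pain medication enrol, and may that patient keep taking it?

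Read literally, the bullet shuts out patients whom inclusion 14 admits, or asks them to stop their analgesic. Section 3.1 itself describes intractable pain as frequent in these patients. Section 10.5 counts any failure to meet a protocol requirement as a deviation that needs corrective action. The same daily opioid dose is thus a deviation under 6.6.1 and permitted under inclusions 9 and 14.

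**Working it through.** The plan gives no figure on this point and no statistical quantity depends on it. The check is a comparison of the current rules, plus differences of the stated intervals.

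**1. The rules side by side**

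| Agent | Section 6.6.1 | Elsewhere |
|---|---|---|
| Opioids in general | Barred in the treatment phase; a later sentence assumes use | Daily pain medication exempt (inclusion 9); users admitted (inclusion 14); use assumed (6.2.4) |
| Long-acting opioids, before ketamine | 12 h | 6 h (inclusion 14 note; end of 6.2.4) |
| Long-acting opioids, after ketamine | 6 h | 6 h (same places) |
| Cannabis, non-routine PRN drugs | 12 h | 24 h (inclusion 9; end of 6.2.4) |
| Benzodiazepines | All barred in the treatment phase | Prohibited above 20 mg/day diazepam equivalents (Synopsis) |
| Alcohol | Barred in the treatment phase | 24 h (inclusion 9; end of 6.2.4) |

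The opioid bullet cannot be read as a dosing-day rule, because it is tied to the treatment phase and the rules in hours follow separately.

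**2. Does the bullet reach eligibility?** Exclusion 14 excludes patients taking drugs prohibited under Section 6.5.1, with a washout of at least five half-lives or as judged clinically. Section 6.5 is Supportive Care and has no subsections. Section 7.1.4 uses the same number for the prohibited-medication list, so 6.6.1 must be meant. Section 6.4 shows a similar slip: it points to 6.1.4 for adverse event management, which now stands in 6.2.4. Section 5 requires eligibility to hold up to dosing. Inclusion 9 sends the reader to the same missing section for its opioid exception, and 6.6.1 contains no exception for short-acting opioids.

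**3. The pre-dose check.** Section 6.2.2 asks staff to confirm 12 h without sedatives but does not define them. The only operative list under that label is the 6.6.1 bullet, which includes every opioid.

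**4. Size of the interval differences**

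- Range of last-dose times on which the rules disagree, longer minus shorter interval: long-acting opioids 12 − 6 = 6 h; cannabis and non-routine PRN drugs 24 − 12 = 12 h.
- Gap without long-acting opioid around one session, pre plus post interval: 6 + 6 = 12 h, or 12 + 6 = 18 h.
- Minimum delay of a dose per session = max(0, gap − dosing interval). The documents give no dosing interval, so 8, 12 and 24 h are assumed:

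| Assumed dosing interval | 6 h rule (gap 12 h) | 12 h rule (gap 18 h) |
|---|---|---|
| 8 h | 12 − 8 = 4 h | 18 − 8 = 10 h |
| 12 h | 12 − 12 = 0 h | 18 − 12 = 6 h |
| 24 h | 0 h | 0 h |

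Under these assumptions, a 12-hourly user can meet the 6 h rule without a late dose if the session is timed 6 h after one. The 12 h rule forces a dose at least 6 h late.

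**The case against.** The strongest reply is that nobody would apply the bullet as written. Four provisions show that opioid users are meant to enrol: inclusions 9 and 14, the end of 6.2.4, and the later sentence of 6.6.1. The Synopsis form of exclusion 14 names antipsychotics and benzodiazepines above a dose limit, but no opioids. Exclusion 14 leaves room for clinical judgement on washout, and Sections 6.5 and 6.6 allow supportive measures generally. The trial has 12 patients at one centre. The 6.2.2 requirements (fully awake, saturation above 92%, more than 8 breaths per minute) and the on-site physician limit the risk of sedation.

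Most of this stands. A reader might infer that the protocol really excludes opioid users; the four provisions and the Synopsis speak against that. What remains is that a general sentence on supportive care does not lift a specific ban that follows it, the Synopsis list is not stated to be complete, and recoverable intent does not settle how a deviation is recorded.

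It is also fair to say that the other intervals are nested: whoever follows the stricter one satisfies both. Applied to opioids in general, though, the stricter rule removes the patients or the analgesia that inclusion 14 allows.

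Two further conflicts might be inferred but are not supported:

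- **Psychostimulants.** Section 6.6.1, which names "methylphenidate, any amphetamines, modafinil, or armodafinil", and Section 6.2.2 agree on 12 h. A conflict with 24 h arises only if these drugs are counted among the psychoactive drugs of inclusion 9 and 6.2.4.
- **Rescue drugs.** Lorazepam and ondansetron in the session are expressly authorised in 6.2.4. That specific provision serves as the exemption, and inclusion 9 concerns what patients agree to refrain from using.

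**Conclusion.** The conflict is real and sits in current operative text. The sedatives bullet of 6.6.1 is a wrong rule on opioids, the three pointers to 6.5.1 lead nowhere, and the long-acting pre-dose interval is stated as both 12 h and 6 h. The consequences are for eligibility, pain control and deviation handling. The interval difference is 6 h per session, giving a gap of 12 h or 18 h; the dose delays rest on assumed dosing intervals.

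Three stronger conclusions are tempting and should not be drawn:

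- **Length of the ban.** Three sessions 2 to 7 days apart span 2 × 2 = 4 to 2 × 7 = 14 days, and a reader might infer that patients would go without opioids for that long. The treatment phase is undefined, so no length can be claimed. The number of opioid users is not given either, so no patient count can be claimed.
- **The completion endpoint.** Nothing in the documents links this wording to session attendance, and no effect on the primary endpoint is claimed.
- **Which benzodiazepine or alcohol rule was meant.** The texts differ, but nothing shows that the looser rule was intended.

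**What to change.** 1. In the 6.6.1 sedatives bullet, replace the blanket opioid wording with: opioids other than a stable pain regimen permitted by inclusion 14. Phrase it so that it also covers that criterion's alternative, opioid use without clinically significant sedation. State in 6.2.2 that the 12 h sedative check does not cover the daily opioid pain medication exempted by inclusion 9; the other 6.2.2 requirements still apply.
2. State one pre-dose interval for long-acting opioids everywhere. Six hours matches inclusion 14 and 6.2.4. If the clinical team prefers 12 h, amend those two places and accept the 18 h gap.
3. Change the 6.5.1 references in inclusion 9, exclusion 14 and Section 7.1.4 to 6.6.1.
4. Set cannabis and non-routine PRN drugs in 6.6.1 to 24 h, to match inclusion 9 and 6.2.4.
5. Ask the clinical team to reconcile the benzodiazepine and alcohol rules, without presuming the looser one. No change is needed for psychostimulants or the in-session rescue drugs.

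**Cost.** A wording amendment with IRB approval before use (Section 10.4), possibly a re-consent determination (Statement of Compliance), and DSMC review under Section 8.4 if the amendment is judged to increase risk. No new visit, procedure or patient is needed.

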## 6.7 Duration of Therapy

Subjects will receive combined treatment until treatment discontinuation criteria is met. Upon meeting treatment discontinuation criteria, subjects will continue on the study in follow-up until study discontinuation criteria are met.

### **6.7.1 Criteria for the Discontinuation of Treatment**

Subjects may withdraw from treatment or the study overall at any time at their request, or they may be withdrawn at the discretion of the Investigator or Sponsor for safety, behavioral reasons, or the inability of the subject to comply with the protocol-required schedule of study visits or procedures. In addition to the drug-specific discontinuation criteria listed in section 6, the following will result in treatment discontinuation:

- Completion of treatment study visits outlined in the Schedule of Events
- The subject or legally authorized representative requests to discontinue the study treatment and/or study procedures;
- Clinical deterioration that, in the opinion of the investigator, increases the risk to the subject;
- Adverse events or intercurrent illness that in the opinion of the investigator warrants the subject's withdrawal from study treatment;
- Significant noncompliance with the protocol schedule or treatment administration in the opinion of the investigator;
- Pregnancy

### **6.7.2 Criteria for the Discontinuation of Study**

Subjects will be taken off study for the following:

- Completed study follow-up period;
- Participant or legally authorized representative requests to be fully withdrawn from the study;
- If, in the investigator's opinion, the continuation of the trial would be harmful to the subject's well-being;
- The subject is lost to follow-up;
- Screen failure;
- Death.

### **6.7.3 Withdrawal of consent**

Subjects are free to withdraw from the study at any time without prejudice to further treatment. Subjects who withdraw consent for further participation in the study will not receive any further study medications or further study observation.

If a subject withdraws consent, they will be specifically asked if they are withdrawing consent to all further participation in the study including any further follow-up (e.g., survival contact telephone calls). Survival status may be obtained from public records for subjects who have withdrawn from any further follow-up contact.

#### **6.7.4 Lost to Follow-Up**

Subjects will be considered lost to follow-up only if no contact has been established by the time the study is completed, such that there is insufficient information to determine the subject's status at that time. Subjects who refuse to continue participation in the study, including telephone contact, should be documented as "withdrawal of consent" rather than "lost to follow-up." Investigators should document attempts to re-establish contact with missing subjects throughout the study period. If contact with a missing subject is re-established, the subject should not be considered lost to follow-up and evaluations should resume according to the protocol.

When a subject is lost to follow-up, site personnel should check hospital records, the subjects' current physician, and a publicly available death registry to obtain a current survival status.

In the event that the subject has actively withdrawn consent, the survival status of the subject can be obtained by site personnel from publicly available death.

